### **Safety**

We will ensure that appropriate plans are in place to guarantee the safety of enrolled subjects. All patients will be made aware of the possible risks associated with treatment group to which they are randomly assigned, as well as the risks inherent in experiencing postoperative pain. For instance, both groups are at risk of experiencing OUD symptom exacerbation. The use of opioid agonists and perioperative pain itself may be risks for OUD symptom exacerbation and relapse. Reduction of buprenorphine to 8 mg before surgery as well as full dose buprenorphine continuation can potentially lead to OUD relapse since exposing patients to opioids with similar properties to the agents they abused in the past as management of their acute post-surgical pain can serve as a trigger for relapse. However, this risk is inherent in the current MMC standard of care.

Another potential risk is difficult post-operative pain control due to buprenorphine continuation since the pharmacokinetics of buprenorphine may interfere with the effectiveness of full opioid agonists used for pain control. However, this risk is not greater than the current risk to patients, since full dose buprenorphine continuation is a practice endorsed by SAMHSA. If patients experience poorly controlled pain, they will receive opioid and non-opioid rescue analgesic agents such as nerve blocks or epidurals when indicated, ketamine infusions, and alpha agonist medications, as determined necessary by the treatment providers caring for the

patient. All participants will be transitioned back to their regular dose of buprenorphine when postoperative surgical pain has subsided as determined by their buprenorphine provider following hospital discharge. This transition will be coordinated with their buprenorphine provider, which is our current standard practice when buprenorphine is discontinued, or the dose is reduced, perioperatively.

### ***Data Integrity and Privacy Protection***

Our study will use a data safety monitoring board (DMSB) that will be scheduled to meet once the study reaches 50% enrollment and in response to any adverse event. The DSMB will review the progress of the study, monitor data, identify any inconsistencies or errors in data collection, and review patient safety. Any errors in data collection that are identified will be reconciled immediately to ensure the validity of our findings. The DSMB will also ensure that this study will not continue to enroll patients if one treatment modality shows early and significant superiority. Below is a table of major and minor adverse outcomes (AEs) that will be reported to the DSMB during the study period and the actions that will be taken. Any unanticipated adverse events will be reported within 7 days. For patients who experience AEs related to substance use in the outpatient setting, [name] will provide patients with information regarding community resources available to patients- such as support groups and harm reduction resources. Study staff will contact the patient's buprenorphine provider on record, as well.

Table 1: Major and Minor Adverse Events

|          | Item  | Action   | Regulatory Reporting   |
|----------|---|--|--|
| Major AE | 1. ED admission due to severe pain
2. Intractable Pain   | Alert acute pain service (APMS) for management recommendations   | Immediate to DSMB; Within 7 days to IRB                            |
|          | 3. Opioid misuse/relapse
4. Opioid overdose
5. Opioid Withdrawal                                | Alert buprenorphine provider on record immediately; provide patients with community resources to seek help as needed |  |
| Minor AE | 1. Hospital discharge delay due to poor pain control
2. Pain worse than anticipated
3. Cravings | Alert integrated medication assistance treatment (iMAT) team and APMS as needed                                      | Within 30 days of event to DSMB; DSMB reports to IRB within 7 days |

The DSMB will determine study stop rules; however, we will recommend to them that when 10 patients have been enrolled in each group (25% enrollment), if >7 in either group have intractable pain interfering with hospital discharge or opioid overdose within 2 weeks of discharge, the study should be terminated. The DSMB members are [name] (Dept. of Anesthesiology); [name] (Dept. of Anesthesiology); [name], NP (Psychiatric Nurse

Practitioner); [name] (Inpatient Psychiatry Consultation-Liaison Team) ; [name] (Senior Biostatistician, MMCRI/CORE); and [name] (Family Medicine, Maine Medical Partners, graduate of MMC Addiction Medicine Fellowship). [name] (Faculty Scientist, Critical Care Pharmacy) will be the medical monitor for this study.

All phases of this study will comply with Health Insurance Portability and Accountability Act (HIPAA) regulations. Data will be collected and stored in a REDCap database to preserve privacy and confidentiality. The 30-Day Timeline Followback will be completed on Timeline, a website (<https://www.smashlabs.org/timeline>) developed and supported by Brown University. Please also refer to the PDF copies of this data collection tool included in the IRBNet package. The responses on the Timeline website will be identified by study numbers only, no PHI will be collected or stored on this site. Information regarding substance abuse history, including illicit narcotic use, will remain confidential and personal identifiers will be removed during data storage. Only members of the research team will have access to the data that participants have consented to provide. Participants will be informed that they have the right to not answer any question that makes them feel uncomfortable.

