### ***Biostatistical Analysis***

#### **Sample Size:**

We estimated study size based on postoperative pain scores in a recent study of surgical patients at our institution (manuscript submitted); mean NRS was  $50 \pm 28$ . Our estimate for effect size is based on published data showing that a difference in NRS of 20/100 points is clinically significant. A sample size of 32 per group will have 80% power to detect a difference in means of 20 (the difference between a Group 1 mean,  $m_1$ , of 50 and a Group 2 mean,  $m_2$ , of 30) assuming the common standard deviation is 28 using a two group t-test with a 0.05 significance level. To account for dropout, we will enroll an additional 8 patients for each group for a total sample size of 80 patients.

Statistical Analysis:

Data will be summarized using descriptive statistics and will be presented as means (SD), medians [IQR] or frequency counts (%), as appropriate. Data will be analyzed on an intention to treat basis. We will first examine the success of randomization by comparing covariates demographic and clinical covariate measurements between the FULL-BUP and STD-BUP groups; to conserve study power, no formal statistical comparison will be performed and the data will be reviewed visually. Next we will perform univariate analyses to compare outcome measures between the FULL-BUP and STD-BUP groups, using a two-sided t-test or Mann Whitney U test for continuous variables and chi square or Fisher exact tests for categorical data, as appropriate. For paired analysis of pre/post surgery instruments, we will use McNemar's test or the Wilcoxon test, as appropriate. We will then explore the relationships between demographic and clinical variables and outcome measures in bivariate analyses, using the above methods or Pearson's and/or Spearman's correlation, ANOVA or Kruskal-Wallis test, as appropriate. Finally, we will explore further any observed differences in outcome measures between study arms by adjusting for covariates using analysis of covariance or (in the event of missing data), mixed models regression. Covariates will be entered into the model if they demonstrate a significant ( $p \leq 0.1$ ) association with outcome measures in bivariate analyses.

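### The recommended safety stop is keyed to enrolment instead of completed follow-up, has no DSMB review tied to it, and counts opioid overdose together with intractable pain

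*Combined protocol and SAP*

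**What the plan says.** All of this is in the protocol section Data Integrity and Privacy Protection unless noted.

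- **Status of the rule.** It is a recommendation: "The DSMB will determine study stop rules; however, we will recommend to them" a termination rule.
- **Timing of the look.** "when 10 patients have been enrolled in each group (25% enrollment".
- **Trigger.** "if >7 in either group have intractable pain interfering with hospital discharge or opioid overdose within 2 weeks of discharge". More than 7 means at least 8 of 10.
- **DSMB meetings.** The board is "scheduled to meet once the study reaches 50% enrollment and in response to any adverse event".
- **Table 1.** Intractable pain and opioid overdose are major adverse events, reported "Immediate to DSMB; Within 7 days to IRB". A separate entry, "Hospital discharge delay due to poor pain control", is minor, reported "Within 30 days of event to DSMB; DSMB reports to IRB within 7 days".
- **Size and pace.** Under Sample Size, "we will enroll an additional 8 patients for each group for a total sample size of 80 patients". Study Timeline and Future Plan expects recruitment to take 11 months.
- **Enrolment before surgery.** The recruitment section places the pre-surgery clinic visit up to two months before the procedure and requires consent before the day of surgery. It does not state the usual interval from enrolment to surgery.

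Neither an expected event rate nor any trigger probability is given for the rule.

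**The concern.** The rule sets its look by a count of enrolled patients, but the outcome it counts matures only after surgery, discharge and up to two further weeks. A patient enrolled but not yet operated on cannot contribute an event, yet is one of the ten. Events still to come therefore look like non-events, and the arm looks safer than it may be.

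Two features add to this. The only enrolment-based DSMB meeting comes at twice the enrolment of the look, so nothing in the schedule produces a count by arm at 25%. And a single limit covers two outcomes of very different gravity, so a limit set with difficult pain in mind also becomes the limit for overdose.

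This is the only numerical safety limit I found in the plan; the interim boundary in Biostatistical Analysis concerns a difference in pain scores. A board that adopts the recommendation unchanged would have a safeguard read on incomplete data, without knowing how often it would act.

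**Working it through.** **1. The plan's own figure.** Total 2 × (32 + 8) = 80. Two groups of 10 make 20, and 20/80 = 25%. The stated enrolment share reproduces.

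**2. Open windows at the 20th enrolment.** Assume uniform accrual: 80/11 = 7.27 patients a month, or 7.27/30.44 = 0.239 a day. The 20th patient enters at 20/7.27 = 2.75 months and the 40th at 5.5 months. Windows still open = 0.239 × (lag to surgery + hospital stay + 14 days). The lag and stay are assumptions; the stay is set to zero here, and a 3-day stay adds about 0.7.

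| Lag to surgery | Calculation | Open windows, of 20 |
|---|---|---|
| 0 days | 0.239 × 14 | 3.3 |
| 14 days | 0.239 × 28 | 6.7 |
| 30 days | 0.239 × 44 | 10.5 |
| 60 days | 0.239 × 74 | 17.7 |

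The 2-week clause may qualify overdose only. The pain component is then incomplete only for patients not yet operated on or discharged: 0.239 × lag, or 0 with no lag, 3.3 at 14 days and 7.2 at 30 days.

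If 3 of the 10 in an arm have not had surgery, at most 7 can have an event, and the arm cannot reach 8 at that reading. The expected number not yet operated on reaches 6 of 20, or 3 per arm, at a lag of 6/0.239 = 25 days.

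**3. Chance of triggering with complete data.** With X binomial(10, p) in one arm, P(X ≥ 8) = 45p⁸(1−p)² + 10p⁹(1−p) + p¹⁰. At p = 0.5 this is (45 + 10 + 1)/1024 = 0.0547. For either arm, with both at the same rate, it is 1 − (1 − P)². The rates are assumptions.

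| True pooled rate | One arm | Either arm |
|---|---|---|
| 30% | 0.2% | 0.3% |
| 40% | 1.2% | 2.4% |
| 50% | 5.5% | 10.6% |
| 60% | 17% | 31% |
| 70% | 38% | 62% |
| 80% | 68% | 90% |

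One arm has an even chance of triggering only at a true rate of about 74%.

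**4. Overdose within the pooled count.** Seven overdoses and no intractable pain in an arm give a count of 7, which is not more than 7. At an assumed overdose rate of 10%, the chance of at least one in 10 patients is 1 − 0.9¹⁰ = 65%; the chance of at least 8 is about 4 in 10 million.

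**5. Table 1 against the rule.** The rule's pain component is intractable pain that interferes with discharge. Table 1 has a major entry for intractable pain and a minor entry for discharge delayed by poor pain control. One patient could be filed under either, and so reach the DSMB immediately or up to 30 days later.

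**The case against.** The strongest reply is that the plan does not leave the board idle until 50%. The DSMB is also to meet in response to any adverse event, and overdose and intractable pain are reported to it at once. A reader might infer from the pooled count that overdoses would pass without review. The documents do not support that: one overdose is enough to prompt a meeting, the board's remit includes patient safety, and it sets its own stopping rules. This part of the reply stands. What remains is that a meeting prompted by a case is not a count by arm at a defined data cut, and the recommended rule would still not be met.

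A reader might also infer that the rule almost never fires. That is so only for pooled rates up to about 40%; at 60% to 80% one arm triggers 17% to 68% of the time. A stopping rule should rarely fire at tolerable rates, and the plan does not say which rate is intolerable. Low trigger probabilities alone are therefore not a defect; the gap is that none were given.

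Nor do the documents show that most of the first 20 would be unoperated. Two months is the outer limit for the clinic visit, not the usual interval from enrolment to surgery. The wording could also be read as naming a cohort, the first 10 per group, followed to 2 weeks after discharge. That reading is reasonable, but the text does not state it, and no data cut or meeting is set to carry it out.

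**Conclusion.** The point holds as a cheap improvement. Three defects rest on the text alone: the look is timed by enrolment while its outcome runs to 2 weeks after discharge; no DSMB review or data cut is tied to it; and overdose has no count of its own. The two Table 1 entries that overlap the rule's pain component must also be reconciled.

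The size of the timing problem depends on an unstated lag: about 3 of 20 windows open with no lag, 7 at 14 days and 11 at 30 days, under uniform accrual. The trigger probabilities depend on an unstated event rate and assume independent patients with complete follow-up. The material does not show that the trial lacks safety oversight before 50% enrolment, nor that the limit of 8 is wrong. That choice belongs to the DSMB.

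**What to change.** 1. State that the count is read when the 10th patient in each group has completed 2 weeks after discharge.
2. Schedule a DSMB review at that data cut, in addition to the meeting at 50% and the event-driven meetings.
3. Tally opioid overdose separately from intractable pain.
4. Reconcile the Table 1 entries so that an event counted by the rule has one class and one reporting time.
5. Optionally, give the DSMB the trigger probabilities over a range of rates before enrolment starts, so that it sets each limit knowing how often it would act.

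The limits remain the DSMB's decision.

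The cost is a wording change and one extra review of 20 patients, plus a one-page table if item 5 is adopted. No patients are added. The look comes somewhat later: under the same accrual assumption, enrolment would by then stand at about 20 + 3 = 23 with no lag, 27 with a 14-day lag and 31 with a 30-day lag. Even at 60 days it would be about 38, still short of the 40 that prompt the 50% meeting. Event-driven reporting continues meanwhile.

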### ***Randomization Plan***

Enrolled participants will be randomized 1:1 into one of two groups (defined below). The randomization scheme will be developed using NQuery Software (Statistical Solutions, Boston, MA).and will use permuted blocks of 4 and 6 patients to ensure balance between study arms. The analyst will provide the research coordinator with randomization assignments in sequentially-numbered opaque envelopes (one series of envelopes for each stratum of anticipated post-surgical pain) . The study coordinator will pass the next envelope in sequence to another member of the study team when it is time to assign a subject to a group. Gerbershagen et. al. documented the distribution of pain scores for 179 different surgical procedures and we will use these data to establish randomization strata. For true practice generalizability on the association between buprenorphine management and postsurgical pain control, we will include surgical procedures based on average pain intensity on postoperative day (POD) 1, as opposed to limiting our criteria to a particular surgical type (see Appendix 1).

Patients will be stratified according to their anticipated pain score on POD 1 (4-6/10 range vs >6/10 range) and those within each stratum will be randomized to one of two groups as follows:

- FULL-BUP group: buprenorphine formulation continued throughout the perioperative period
- STD-BUP group: buprenorphine formulation reduced to 16mg the day prior to surgery and then 8mg on the day of surgery onwards. Participants in this group taking 12-16mg buprenorphine at baseline will have no change to their buprenorphine dose on the day prior to surgery.

All participants will be transitioned back to their regular dose of buprenorphine when postoperative surgical pain has subsided as determined by their

buprenorphine provider following hospital discharge. This transition will be coordinated with their buprenorphine provider, which is our current standard practice when buprenorphine is reduced perioperatively.

As the study is unblinded, both patients and providers will be aware of the randomization assignment. To help mitigate bias, the team members collecting and entering data will be masked regarding the patient's assignment. The REDCap database has the randomization assignments in an instrument separate from the study data collection instruments, allowing for data entry without seeing which group the subject is in.

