Intraoperative opioid consumption, type of anesthesia, total PACU opioid consumption, normalized for time spent in PACU, and 24, 48 up to 72-hour opioid consumption will be extracted from the patients' charts. All opioid consumption will be converted into MME. One month postoperatively, participants will receive virtually- administered questionnaires, including: a substance use evaluation, where they will be asked to complete self-assessments identical to those administered on the day of surgery for comparison analysis. Patients will be encouraged to record postoperative pain and opioid consumption on the Timeline website regularly and reminded that compensation is tied to completion. Reminder phone calls will be made by study staff during this time period.

We will contact each participant's buprenorphine provider to collect data for buprenorphine treatment retention following surgery and will assess each patient's Maine Prescription Awareness Tool (MainePAT) record to collect data for outpatient opioid utilization during the 30 days following surgery. Buprenorphine formulations will not be included in our MME total.

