#### Measures for Aim 1 (Pain scores)

The primary outcome of this study will be composite pain scores 24 hours after surgery. Others have shown that composite pain scores quantify pain with greater accuracy than a single measurement. Jensen et. al. concluded in their study that composite pain intensity scores from two or more individual ratings of pain are valid for detecting treatment effects. Pain scores will be measured using a numeric rating scale (NRS) (0=no pain; 10= worst possible pain). "Worst," "average," and

“least” pain scores will be assessed for the preceding time interval at 24, 48, and 72 hours following surgery. Inpatient pain scores will be collected as part of routine post-operative care and will be extracted from the medical record; there is no set protocol for routine pain score collection but typically it is done every 4-8 hours. To collect pain scores, nursing staff asks patients to rate their current pain on a scale from 0-10. If a participant is discharged prior to 72 hours after surgery, NRS scores will be assessed at the remaining time points via telephone. Prior to discharge, study staff will provide patients with a log to keep a record of their pain scores, at least once every 8 hours, in order to mitigate recall bias in anticipation of being contacted by research staff. Study staff will call discharged patients and ask them to report their pain scores for each 24 hour period between discharge and 72 hours postoperatively as recorded on the forms they were given at time of discharge.

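### Overdose, relapse, withdrawal and ED admission call for immediate action, but no described contact asks about them between 72 hours and one month, so they surface late or not at all

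*Combined protocol and SAP*

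**What the plan says.** **Duties.** Table 1 lists ED admission due to severe pain, opioid misuse/relapse, overdose and withdrawal among the major adverse events. As extracted, its reporting column has all major events going to the DSMB at once and to the IRB within 7 days. For misuse/relapse, overdose and withdrawal the action is "Alert buprenorphine provider on record immediately; provide patients with community resources to seek help as needed". The text below the table recommends that, at 10 enrolled per group, if more than 7 in either group have "intractable pain interfering with hospital discharge or opioid overdose within 2 weeks of discharge, the study should be terminated".

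**Contacts.** Under Measures for Aim 1, staff call discharged patients for pain scores "for each 24 hour period between discharge and 72 hours postoperatively". Measures for Aim 2 adds calls about pain medication taken over the same period. Study Procedures then places virtual questionnaires at one month. For the interval it encourages Timeline entries on pain and opioid consumption and adds: "Reminder phone calls will be made by study staff during this time period". No dates, number or adverse-event content are given for these calls.

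**Other sources.** Buprenorphine providers are contacted about treatment retention, with no timing given. MainePAT supplies opioid dispensing over 30 days. The described chart extraction covers anesthesia type, inpatient pain scores and opioid consumption up to 72 hours.

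**The concern.** An immediate duty to report or alert works only if someone learns of the event. As described, an overdose or relapse after the 72-hour call reaches study staff before one month only if the participant, a provider or a clinician volunteers it. The Safety section accepts that both arms carry a relapse risk, and the Significance section lists withdrawal, cravings and relapse among the secondary outcomes, so incomplete capture affects the results as well as oversight. The DSMB would see whichever events happened to be volunteered and could not tell a quiet trial from an unobserved one.

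**Working it through.** **Plan's own figure.** The stop-rule look is at 10 per group: (10 + 10)/80 = 25% of enrollment, as stated.

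**Step 1: duties against detection after 72 hours.**

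| Table 1 event | Immediate duty | Described means of detection after 72 hours |
|---|---|---|
| ED admission for severe pain | DSMB report | No question or record check |
| Misuse/relapse | DSMB report, provider alert | Timeline entries with no assigned reviewer; one-month misuse, craving and Timeline Follow-Back instruments |
| Overdose | DSMB report, provider alert, stop-rule count | No question or record check |
| Withdrawal | DSMB report, provider alert | Withdrawal scale named for the day of surgery; possibly repeated at one month, since Study Procedures repeats the day-of-surgery self-assessments |

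The described one-month instruments cover craving, misuse, depression and substance use. None has a described overdose or ED item, so for those two events the gap does not close at day 30.

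**Step 2: length of the gap.** Inputs: last early calls at 72 hours (day 3), one-month session taken as day 30, and a window of 14 days from discharge.

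- Gap: 30 − 3 = 27 days.
- Part of the overdose window after the last call: 14 − 3 = 11 days if discharge is on day 0, and all 14 days if discharge is on day 3 or later.
- Wait until the one-month session, with discharge on day 0: 30 − 3 = 27 days for an event just after the last call, 30 − 8 = 22 days for one on day 8, and 30 − 14 = 16 days for one at the end of the window.
- Accrual in the gap, assuming a uniform rate (80 patients in 11 months, Study Timeline): 80/11 = 7.3 per month, so 7.3 × 27/30 ≈ 6.5, or 6 to 7 further patients.

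**Step 3: effect on the stop rule.** More than 7 of 10 means at least 8. With a true combined event rate p and a share a of events found, one arm triggers with probability P(X ≥ 8), X ~ Binomial(10, p·a). The rates are assumptions, and events are taken as independent.

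| p | a = 1 | a = 0.75 | a = 0.5 |
|---|---|---|---|
| 0.8 | 0.678 | 0.167 | 0.012 |
| 0.5 | 0.055 | 0.008 | 0.0004 |
| 0.2 | 0.00008 | < 0.0001 | < 0.0001 |

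For either arm at p = 0.2 with every event found: 1 − (1 − 0.000078)² = 0.00016. Missed events change the result only where half or more of an arm has an event. Even that overstates the effect, because a is applied to all events, whereas intractable pain that interferes with discharge is seen in hospital. Only the overdose part depends on post-discharge follow-up.

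**Step 4: a conflict inside the document.** The Limitations section says participants will be told that the drug-use information they provide stays out of their patient record and that their providers will not have access to it. Table 1 requires staff to "Alert buprenorphine provider on record immediately" for misuse or relapse. Both cannot hold for a relapse that a participant reports to study staff, and the two passages must be reconciled.

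**The case against.** - **Unseen material.** Study Procedures refers the reader to the protocol schema. That figure, and the text between the statistical analysis and Limitations sections, could not be read here. A contact listed only there cannot be excluded. This stands as a limit on the finding.
- **The stop rule.** A reader might infer that the gap disables it. The documents do not support that: the DSMB sets the rules, the quoted one is a recommendation, and Step 3 shows that missed overdoses would almost never decide it. The objection stands.
- **Relapse is late, not lost.** Timeline Follow-Back is a calendar method for substance use. Repeated at one month, it records a day-8 relapse in anyone who completes it. This stands for completers, but not for non-responders, overdoses or ED admissions.
- **Bias between arms.** A reader might infer that STD-BUP participants have more provider contact, since they have a dose change to reverse: "This transition will be coordinated with their buprenorphine provider". But the plan says that about all participants, and staff contact every participant's provider. With unblinded arms, unequal reporting is possible, but nothing in the documents shows it. Overdose is not a listed outcome, so no planned efficacy comparison rests on it.
- **A missed percentage.** A reader might take the dropout allowance (8/40 = 20%) as one-month non-response and derive a share of relapses missed. That allowance belongs to the sample size for pain at 24 hours, and the plan gives no relapse rates.
- **Immediate from awareness.** The duties can fairly be read as running from when staff learn of the event. That settles compliance, but leaves how staff are to learn of it unanswered.

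**Conclusion.** The point holds as a gap in safety ascertainment. In the text that could be read, no scheduled contact asks about overdose, ED admission, relapse or withdrawal for about 27 days after the 72-hour calls. No overdose or ED item, and no later chart check, is described even at day 30. Relapse in participants who complete the one-month Timeline Follow-Back is recorded late. Overdose, ED admission and events in non-responders may not be recorded at all.

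The main consequences are late alerts to the DSMB and providers, and a safety summary of unknown completeness. The interval is not free of contact: reminder calls and Timeline entries exist, but they have no dated adverse-event content and no assigned review. The conclusion assumes one month means about day 30 and that the schema and the unread text add no adverse-event contact. It is a worthwhile, low-cost improvement and does not affect the primary analysis or the sample size.

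**What to change.** In Study Procedures and in Data Integrity and Privacy Protection:

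1. Date one of the reminder calls at about day 14 after discharge. Add an identical short adverse-event script in both arms to that call and to the day-30 session, covering ED admission or readmission, overdose, misuse/relapse and withdrawal.
2. At both times, check the Epic record for these events for every randomised participant, including those not reached.
3. State that the by-arm safety table and any stop-rule count use these checks.
4. Reconcile the Limitations promise on provider access to drug-use reports with the provider alert in Table 1 before the script is used, since asking about relapse makes the conflict concrete.

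The cost is protocol wording, a short form and a few minutes of staff time per participant. The reminder calls are already planned and study staff already extract data from charts, but the day-14 date and the later chart check are new. Reported event counts will probably rise somewhat, because events are being sought.
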